Our sample size calculation (see table below) is based on the results from the pilot study with the primary outcome being change in TUG. We powered our original study based on existing literature, in which the mean TUG score for individuals with PD is 14.8 seconds with standard deviation of 5.8 seconds, and minimum clinically important difference values for the TUG ranged from 2 seconds to 5 seconds in various studies.^{1,17} However, our pilot cohort had a pre-intervention baseline mean TUG of 9.6 seconds, standard deviation of 2.1. As per the tables below, if our new cohort has a similar baseline mean TUG, we would need 12 individuals in each arm to detect a difference of 2 seconds with 90% power, however this may not be plausible (i.e., 9 seconds may be close to the limit of how quickly anyone can complete the TUG task). If, however, participants have a more modest baseline to start, which may be expected when recruiting more broadly than at a tertiary referral center, we yield the second half of the table below. Here, we are extrapolating a baseline mean TUG of 12.5 with SD 4.0 (between our pilot data and the existing literature); with 19 individuals per arm, we would be 90% powered to detect a 3s difference between pre- and post-intervention TUG.

If we assume up to 25% attrition in this group of older adults with a chronic neurodegenerative disease, particularly in a longitudinal study over six months, we need to enroll 52 individuals (26 per arm) to yield a total of 40 completing the study.

Baseline mean TUG	Baseline SD TUG	Minimum clinically Important difference	Power	Sample size per arm
9.6	2.1	2s	.9	12
			.8	9
9.6	2.1	3s	.9	6
			.8	4
9.6	2.1	4s	.9	3
			.8	3
9.6	2.1	5s	.9	2
			.8	2
12.5	4.0	2s	.9	43
			.8	32

12.5	4.0	3s	.9	19
			.8	14
12.5	4.0	4s	.9	11
			.8	8
12.5	4.0	5s	.9	7
			.8	6

II.b. Gender of Subjects

There will be no exclusion of subjects based on gender.

II.c. Age of Subjects

Subjects will be 30-90 years of age.

II.d. Racial and Ethnic Origin

There will be no exclusion of subjects based on racial or ethnic characteristics. However, subjects must be fluent in English to participate in the karate classes, as that is the language of instruction, and due to the general lack of appropriately translated neurological and neuropsychological assessments and appropriate normative comparison samples. These factors are critical for accurate administration, scoring, and interpretation of neurological and neuropsychological test data.

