Data will be exported from REDCap in de-identified format for statistical analysis, with all PHI stripped from the dataset prior to analysis by statisticians. We will summarize categorical variables by frequencies and percentages and will assess continuous variables for normality, summarized by mean/standard deviation, or median/interquartile range. We will report the basic descriptive statistics of the cohort, including baseline demographics, TUG, MDS-UPDRS, HADS, PDQ-8, IPAQ, SDMT, MoCa, and DST. We will report on attendance, defined as the percentage of classes attended, in each arm once active. We will analyze the change in TUG, MDS-UPDRS, HADS, PDQ-8, IPAQ, SDMT, DST, MoCa, and PAGEQ respectively, from baseline to six months, comparing Arm 1 and 2 (active vs. control), and again at twelve months to determine whether longer participation yields additional benefits, using paired *t*-tests or nonparametric Wilcoxon sign rank tests, as appropriate. We will report on the percentage of subjects endorsing each of the 7 PGIC response options at six and twelve months, between Arms, respectively. We will report the descriptive statistics concerning whether subjects’ individual predefined goal for the class was achieved (binary outcome), and will present de-identified qualitative comments noted in the feedback at the study visit focus groups. We will report descriptive statistics on continued interest and likelihood of recommending the program to someone else with PD. We will analyze descriptive statistics on continued involvement in karate/martial arts, and will again report the percentage of subjects endorsing each PGIC response option.

The qualitative data from the study visit focus groups will be audio-recorded and transcribed, with all identifying information stripped from the transcripts. Once transcribed, the audio recordings will be destroyed. The qualitative data will be analyzed using a grounded theory approach to identify pertinent themes, with data stored as password-protected files behind the Rush firewall, accessible only to study staff.

All video footage will be the sole property of the PI. Videos will have identifying information (i.e. image of patient’s face, first name). Video files will be stored and password-protected behind the Rush and the Columbia firewalls. The video along with the data collected from the focus groups and karate classes may be used as part of the dissemination of the study results and for educational purposes.

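### The TUG sample-size table uses a known-variance z formula although the plan names a paired t or signed-rank test, so on its own inputs the printed powers are too high: modestly at the row that sets enrolment, badly only in rows that do not

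*Combined protocol and SAP*

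**What the plan says.** Section II.a (Number of Subjects) bases the sample size on TUG, "with the primary outcome being change in TUG". Its table has 16 rows: two standard deviations, four differences and two powers.

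- The upper half uses the pilot: "our pilot cohort had a pre-intervention baseline mean TUG of 9.6 seconds, standard deviation of 2.1". From it the text concludes that "we would need 12 individuals in each arm to detect a difference of 2 seconds with 90% power", then doubts that a 2 s gain is plausible in so fast a cohort.
- The lower half rests on an interpolated population: "we are extrapolating a baseline mean TUG of 12.5 with SD 4.0". This gives the row that sets enrolment: "with 19 individuals per arm, we would be 90% powered to detect a 3s difference between pre- and post-intervention TUG".
- The differences of 2 to 5 s come from the literature: "minimum clinically important difference values for the TUG ranged from 2 seconds to 5 seconds in various studies".
- Allowing for up to 25% attrition, the section enrols 52 (26 per arm) and expects 40 completers.

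The section names no formula, alpha or sidedness, and the table labels its SD as a baseline SD.

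Section III.b (Data Analysis and Data Monitoring) analyses change in TUG to six months and again at twelve, "using paired *t*-tests or nonparametric Wilcoxon sign rank tests, as appropriate", and describes the six-month analysis as a comparison of the active and control arms.

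**The concern.** A known-variance formula sets the critical value at 1.96 whatever the sample size. A paired t-test estimates the SD from the data, and its two-sided 5% critical value is 2.10 with 19 pairs, 2.20 with 12 and 12.7 with 2. A signed-rank test uses ranks and has a smallest attainable p-value fixed by the number of pairs. If the table was built on the z criterion, its powers belong to a test the trial does not plan to run.

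At stake are the accuracy of the 90% claim behind the enrolment target, and the credibility of rows that offer 80 to 90% power with 2 to 4 people per arm.

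**Working it through.** **Inputs.** SDs of 2.1 and 4.0 s, differences of 2, 3, 4 and 5 s, powers of 0.9 and 0.8, and the printed sizes, all from Section II.a; the tests from Section III.b. Two assumptions are needed because the plan does not state them: two-sided alpha 0.05, and the printed SD standing for the SD of pre-post change.

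**Step 1: reproduce the table.** Use n = ((1.96 + z_power) × SD/difference)², rounded up, with z_power = 1.282 for 90% and 0.842 for 80%.

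- SD 2.1, 2 s, 90%: (3.242 × 1.05)² = 11.6, so 12.
- SD 4.0, 3 s, 90%: (3.242 × 1.333)² = 18.7, so 19.

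All 16 rows match. One-sided z, paired t (one- or two-sided) and two-sample z each fail to reproduce the table. The attrition step also matches: 19/0.75 = 25.3, so 26 per arm and 52 in total.

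**Step 2: power of the paired t-test at the printed sizes.** Power comes from the noncentral t with n − 1 degrees of freedom and noncentrality (difference/SD) × √n. At n = 19 the noncentrality is 0.75 × √19 = 3.27, the critical value is 2.10 and power is 0.871.

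| SD (s) | Difference (s) | Printed power | Printed n | Paired-t power | n needed by t |
|---|---|---|---|---|---|
| 2.1 | 2 | 90% | 12 | 85.1% | 14 |
| 2.1 | 2 | 80% | 9 | 70.7% | 11 |
| 2.1 | 3 | 90% | 6 | 79.7% | 8 |
| 2.1 | 3 | 80% | 4 | 49.7% | 7 |
| 2.1 | 4 | 90% | 3 | 44.1% | 6 |
| 2.1 | 4 | 80% | 3 | 44.1% | 5 |
| 2.1 | 5 | 90% | 2 | 20.8% | 5 |
| 2.1 | 5 | 80% | 2 | 20.8% | 4 |
| 4.0 | 2 | 90% | 43 | 89.3% | 44 |
| 4.0 | 2 | 80% | 32 | 78.2% | 34 |
| 4.0 | 3 | 90% | 19 | 87.1% | 21 |
| 4.0 | 3 | 80% | 14 | 73.7% | 16 |
| 4.0 | 4 | 90% | 11 | 84.8% | 13 |
| 4.0 | 4 | 80% | 8 | 68.1% | 10 |
| 4.0 | 5 | 90% | 7 | 78.6% | 9 |
| 4.0 | 5 | 80% | 6 | 68.9% | 8 |

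All 16 fall short, 12 of them by 5 points or more. The gap runs from 0.7 points (n = 43) to 69 points (n = 2). With 20 completers per arm, the 3 s, SD 4.0 power is 88.9%.

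**Step 3: signed-rank.** Simulated with normal data and exact p-values, power is about 85 to 86% at n = 19, about 87% at n = 20 (3 s, SD 4.0), and about 81 to 82% at n = 12 (2 s, SD 2.1). The smallest two-sided p with n pairs is 2/2ⁿ: 0.5, 0.25 and 0.125 at n = 2, 3 and 4; 0.0625 at n = 5; 0.031 at n = 6. The five rows printed with n of 4, 3, 3, 2 and 2 therefore have no power at 0.05 by that test, whatever the SD.

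**Step 4: how far the result depends on the SD.** With equal SDs before and after, SD of change = SD × √(2(1 − r)), where r is the pre-post correlation. The printed SD equals the SD of change only if r = 0.5. The pilot's change from 9.6 to 9.0 s with p = 0.12 in 15 completers, if it came from a paired t-test, implies t = 1.656 and an SD of change of 0.6 × √15/1.656 = 1.40 s. That is 0.67 of the baseline SD, or r of about 0.78. Applying that ratio to both halves of the table, paired-t power reaches the printed level in 12 of 16 rows (99.6% at n = 19); only the n = 2 and n = 3 rows stay short. At r = 0.55, n = 19 already gives 90.3%.

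**Step 5: the between-arm comparison.** With an SD of change of 4.0 s and a 3 s difference between arms, two-sample t power (2n − 2 degrees of freedom, noncentrality 0.75 × √(n/2)) is about 61% at 19 per arm and 64% at 20. The z version at 19 gives about 64%.

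**The case against.** The best defence has four parts.

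1. **The SD matters more than z versus t.** This stands. A reader might infer from the table that the trial lacks 90% power for a 3 s pre-post change. The documents do not support that: they give no SD of change, and Step 4 shows that a slightly higher correlation than 0.5 removes the shortfall. What remains is that the table is wrong for the inputs it prints.

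2. **The operative gap is small.** This also stands. It is 2.9 points at 19 and 1.1 at 20 completers by t, on an SD the plan itself calls extrapolated. It changes no enrolment decision, although the 90% is stated without qualification.

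3. **The extreme rows are not used.** True. A reader might infer that the trial could end with data unable to reach significance by signed-rank. It could not: about 20 completers per arm are planned, signed-rank is only the alternative test, and nobody proposes 2 to 4 per arm. The rows are still printed as valid sizes.

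4. **A corrected table would put precise figures on a within-arm change, while Section III.b compares the arms.** This is fair and limits the remedy. The mismatch between a pre-post sizing and a between-arm comparison is a separate and larger matter. Moving from z to t does not cure it, and a between-arm recalculation with the z formula would repeat the present error.

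The z method and alpha are inferred, but an exact match in 16 of 16 rows makes the inference strong.

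**Conclusion.** The point holds as a conditional statement about the printed table. With two-sided alpha 0.05 and the printed baseline SD taken as the SD of pre-post change, every printed power is too high for the paired t-test. For the row that sets enrolment the overstatement is about 1 to 3 points by t and about 3 to 5 by signed-rank, at 20 and 19 completers per arm respectively. For the 12-per-arm row it is 4.9 points by t. It is large only in small rows that play no part in choosing 52. The impossibility under signed-rank for the five smallest rows needs no assumption about the SD.

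This does not show that the trial is underpowered for a pre-post change. Nor should 87 to 89% be read as power for Arm 1 versus Arm 2, where the same inputs give about 61 to 64%.

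**What to change.** In Section II.a:

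- State alpha and sidedness, and say that the SD used is the assumed SD of change, with its basis.
- Recompute the table from the noncentral t, or by simulation if signed-rank may be used. The t-based sizes are in the last column of the table above.
- Drop rows too small for the named tests. While signed-rank remains an option, that means any row with fewer than 6 per arm.
- Replace the 90% claim with about 87 to 89% at 19 to 20 completers per arm (about 85 to 87% by signed-rank) for a within-arm pre-post change of 3 s with an SD of change of 4.0 s.
- Label that figure as pre-post only, and use t-based power in any between-arm restatement.

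Keep enrolment at 52. Holding 90% by paired t on these inputs would take 21 completers per arm, hence 28 per arm (56 in total) after 25% attrition, but a gap this small on an extrapolated SD does not justify the change. The cost is one table and one sentence, with a slightly less favourable stated power and no added participants or procedures.

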The aim of this study is to test whether and to what degree a community-based karate class tailored for individuals with early- to middle-stage Parkinson's Disease (PD) 1) is feasible; and 2) improves objective mobility and balance, 3) improves patient-reported outcomes in mobility, balance, camaraderie, and overall wellbeing compared with individuals given a standard exercise prescription for PD. The benefits of exercise for general health and wellbeing in older adults are well-established. Balance exercises such as tai chi and yoga, along with resistance training, can improve or maintain physical function in older adults and enhance muscle strength. Furthermore, aerobic activity is critical for maintaining and improving cardiovascular and functional health. Non-contact boxing has seen a surge in popularity among individuals with PD, with components of both aerobic and balance exercise. While participants anecdotally note improvements in stress and physical function, this has only been minimally studied. However, drawing on the enthusiasm for boxing, literature surrounding aerobic and balance exercise in PD, and the combined aerobic, balance, and mindfulness practices that comprise karate, we hypothesized that participation in structured karate programs may offer similar or greater benefits than any of the individual components above. In particular, the aerobic, resistance, and balance aspects of karate may be beneficial for physical and cognitive wellbeing, and the mindfulness exercise may improve overall wellbeing. Therefore, we conducted a pilot, 10 week-long study of a structured karate exercise program for people with early to middle PD during the summer and early fall of 2018. In this single-arm pilot (no control participants), we assessed mobility, gait, balance, falls, attention, quality of life, patient-reported global impression of change, and mood before and after the 10 weeks of karate. Among 15 participants completing 10 weeks of twice-weekly classes, our pilot data highlighted our feasibility: adherence was high (mean attendance 87% of 20 classes), 100% of participants indicated interest in continuing karate classes, and 100% would recommend the program to other individuals with PD, respectively. Additionally, participants experienced a statistically and clinically significant improvement in quality of life, as measured by the Parkinson's Disease Questionnaire-Short Form (PDQ-8), with mean scores improving from 25.3 to 19.3 ($p < 0.01$), significant improvements in measures of working memory and executive function, and a trend toward improvement in the Timed Up and Go mobility measure (9.6 seconds pre-intervention to 9.0 seconds post-intervention, $p = 0.12$). Further data analysis—including qualitative analysis—is underway.

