
Based on these promising results from the pilot, we are therefore proposing the next step in this line of research, namely, a randomized, controlled trial of a structured karate intervention for individuals with PD. Individuals will receive a one-time, in-person training in best practices for exercise in PD. Due to both the capacity of the karate classes and the scientific approach to detecting changes in PD, subjects will be randomly assigned into either **Arm 1**: immediate participation in the karate class or **Arm 2**: participation in usual exercise for six months followed by karate classes for six months. For participants in **Arm 1**, following the first six months of classes, subjects may choose to continue their participation in karate and in the study, though this will require paying membership fees at the *dojo* (karate studio). For participants in **Arm 2**, following the first six months of usual exercise, participants will then begin 6 months of twice-weekly classes. We will conduct in-person assessments of motor function, attention, and cognition at baseline, six months, and twelve months. We will conduct online assessments of adherence to exercise program, quality of life, anxiety, depression, global impression of change, and group cohesion via bimonthly online surveys. We will assess feasibility with measurement of attendance at each class, and sustainability with the rate of attendance among the participants beyond their first six months of classes.

We hypothesize: 1) Subjects will show improved mobility after 6-months of twice weekly karate classes, as measured by change in Timed Up & Go (TUG)¹ and MDS-UPDRS motor subscore; 2) The majority of subjects will report a positive change from baseline in their overall wellbeing, as measured by a response of “very much improved”, “much improved” or “minimally improved” on the Patient Global Impression of Change Scale (PGIC)² following 6 months of classes; 3) Feasibility will be high, as measured by $\geq 75\%$ attendance rate and a response of “yes” to either “Would you recommend this program to someone else with PD?” or “If available, would you continue to participate in this or a similar karate class?”

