After the training, eligible subjects will be grouped by dojo preference, and randomized 1:1 within each dojo into **Arm 1**: immediate participation in six months of twice-weekly karate classes, or **Arm 2**: usual exercise for six months. After six months, Arm 1 participants may opt to pay for dojo membership and continue classes, and Arm 2 participants will crossover and begin six months of twice-weekly karate classes. Only the Research Coordinator will know which subjects belong to Arm 1 and Arm 2, and she/he will deliver all study-related communication to the subjects.

The karate classes have been specifically designed for individuals with early- to middle-stage PD, focused on incorporating upper and lower limb movements in multiple directions, increasing awareness throughout the body, shifting body weight and rotation, relaxation of the muscles, improving reaction time, using complex repetitive actions to improve coordination, footwork training and centered weight shifts to help with fall prevention, and striking shields for self-defense and stress relief. The PI and study team will provide instruction on PD to all instructors prior to study launch, and will be available and responsive to any questions or concerns throughout the course of the study. The structure of the 6-

month curriculum will be identical at each of the five dojo locations. If a subject misses a class, they may choose to make up a class at one of the other dojo locations.

Every two months, subjects in both Arms will receive an online link to report their attendance at classes, indicate whether their PD medication regimen has changed (as a potential confounder), and complete the IPAQ, HADS, and PDQ-8. In addition, the survey will contain the Physical Activity Group Environment Questionnaire (PAGEQ) to measure camaraderie, and Patient Global Impression of Change (PGIC) for the subject's global impression of change. The online survey will be delivered through a secure online database called Research Electronic Data Capture (REDCap). The purpose of the online surveys is to track adherence to karate classes, adherence to other walking/moderate/vigorous activity, quality of life, anxiety, depression, global impression of change, and group cohesion.

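### The 90% power with 19 per arm is for a one-sample pre-post change, not for the randomized comparison of arms, and the paired tests named for that comparison cannot make it

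*Combined protocol and SAP*

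**What the plan says.** **Sample size (II.a).** The basis is given as "Our sample size calculation (see table below) is based on the results from the pilot study with the primary outcome being change in TUG". The table lists baseline mean TUG, baseline SD, a minimum clinically important difference and power, and ends in a column for sample size per arm. For the scenario the trial relies on (baseline mean 12.5 s, SD 4.0 s), the text says that "with 19 individuals per arm, we would be 90% powered to detect a 3s difference between pre- and post-intervention TUG". Allowing for 25% attrition, this becomes 26 per arm, 52 in total. No alpha, sidedness, SD of change, pre-post correlation or expected control-arm change is given.

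**Question and design.** The opening aims are comparative: outcomes are to improve "compared with individuals given a standard exercise prescription for PD". Under I.c, participants are "randomized 1:1 within each dojo into" immediate karate or usual exercise. Hypothesis 1, by contrast, has no comparator: "Subjects will show improved mobility after 6-months of twice weekly karate classes".

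**Analysis (III.b).** Change in TUG and eight other measures is analysed "from baseline to six months, comparing Arm 1 and 2 (active vs. control"), and again at twelve months. The tests given in that sentence are paired t-tests "or nonparametric Wilcoxon sign rank tests, as appropriate". No two-sample test, ANCOVA or mixed model appears anywhere in the document.

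**The concern.** Three parts of the plan answer different questions. The sample size and hypothesis 1 concern change within a person. The aim, the randomization and the words of III.b concern a difference between arms. The named tests go with the first, although the sentence containing them describes the second.

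Two things are at stake:

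- **Power.** N=52 rests on the 90%. A null difference between arms could be taken as the result of a 90%-powered trial, although that power was computed for another quantity.
- **Inference.** Followed literally, III.b leads to a separate pre-post test in each arm. Such tests make no use of the control arm. They cannot separate karate from practice on the TUG, regression to the mean or the exercise training that everyone receives at baseline. A significant change in one arm beside a non-significant change in the other is not evidence that the arms differ.

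**Working it through.** **Inputs.** From II.a: SD 4.0 s (baseline), difference 3 s, power 90%, 19 per arm, 25% attrition, 52 enrolled; pilot baseline SD 2.1 s. From the opening section: pilot TUG "9.6 seconds pre-intervention to 9.0 seconds post-intervention", p = 0.12, n = 15, over 10 weeks. Assumed: two-sided alpha 0.05, which reproduces the table.

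**1. Reproducing the plan's figures.** One-sample normal formula, with the baseline SD used as the SD of the difference:

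n = (1.96 + z_power)² × (SD/difference)²

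where (1.96 + 1.2816)² = 10.51 for 90% and (1.96 + 0.8416)² = 7.85 for 80%.

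- SD 4.0, 3 s, 90%: 10.51 × (4/3)² = 18.68, so 19. Plan: 19.
- SD 4.0, 3 s, 80%: 7.85 × (4/3)² = 13.95, so 14. Plan: 14.
- SD 2.1, 2 s, 90%: 10.51 × (2.1/2)² = 11.58, so 12. Plan: 12.

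Rounded up, all 16 rows match. The two-sample formula doubles n (2 × 18.68 = 37.4, so 38 in the key row) and matches none of them. Attrition: 19/0.75 = 25.3, so 26 per arm. Since 52 × 0.75 = 39, about 19 to 20 completers per arm are expected.

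**2. Power of the comparison between arms.** If the SD is 4.0 at both visits and r is the pre-post correlation:

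- change score: SD of change = 4 × √(2(1 − r)), df = 2n − 2
- ANCOVA on baseline TUG: residual SD = 4 × √(1 − r²), df = 2n − 3

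Power for a 3 s difference (noncentral t, two-sided 0.05):

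| r | Change score, 19 per arm | Change score, 20 per arm | ANCOVA, 20 per arm |
|---|---|---|---|
| 0 | 36% | 37% | 64% |
| 0.3 | 48% | 50% | 68% |
| 0.5 | 61% | 64% | 76% |
| 0.7 | 83% | 85% | 90% |
| 0.75 | 89% | 90% | 94% |
| 0.8 | 94% | 95% | 97% |

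The baseline SD equals the SD of change only at r = 0.5. There, 90% power needs 39 per arm by change score (t-based) or 30 by ANCOVA. At r = 0.7 the figures are 24 and 21; at r = 0.8 they are 16 and 15.

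**3. Break-even for 90%.**

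- 20 per arm: SD of change at most 2.85 s (r at least 0.75), or r at least 0.70 with ANCOVA.
- 19 per arm: SD of change at most 2.78 s (r at least 0.76), or r at least 0.72 with ANCOVA.

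**4. What the pilot suggests.** Assume a paired t-test and equal pre and post SDs. Then p = 0.12 on 14 df gives t = 1.656, the SD of change is 0.6/1.656 × √15 = 1.40 s, and r = 1 − 1.40²/(2 × 2.1²) = 0.78. Rounding alone (change 0.5 to 0.7 s, p 0.115 to 0.125) allows an SD of change of 1.15 to 1.66 s and r of 0.69 to 0.85. With SD 4.0 and 20 per arm, that is change-score power of 83% to 99%.

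**5. The tests.** A paired t or signed-rank test works on differences within one person. Arm 1 and Arm 2 are different people with no pairing, so neither test gives an estimate or a p-value for the difference between arms.

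**The case against.** The strongest reply is that nothing is miscalculated and the sample size may be adequate. The sentence in II.a says openly that it concerns a pre-post difference, which agrees with hypothesis 1 and with paired tests. The one-sample formula with SD 4.0 is algebraically the same as a two-sample change-score formula at r = 0.75, and the only relevant data in the document, the pilot, point to r near 0.78. At that value change-score power is about 92% with 19 per arm and 94% with 20. If the pilot's SD of change itself carried over, its upper 95% confidence limit, even at the unfavourable end of rounding, is 1.66 × √(14/χ²), with χ² the 2.5% point on 14 df, or 2.62 s. That is still below the break-even.

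This stands as a reason not to call the trial underpowered. It does not establish the 90%. The plan neither states nor uses a correlation. The pilot value rests on an unnamed test, 10 weeks of follow-up and a cohort with half the assumed spread. The r range above covers rounding only, and sampling error with 15 people would widen it.

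It is also fair that paired tests suit within-person changes, such as Arm 2 before and after crossover, and that the sentence in III.b says tests are chosen as appropriate and also covers twelve months. But both tests offered are paired, and they are attached to the comparison of arms. If the primary test really is within-person, the control arm has no part in it, which contradicts the stated aim.

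Finally, classes were scheduled for 2019 and the Covid-19 text covers only remaining twelve-month assessments, so recruitment appears to be over. That bears on how the power correction is recorded, not on whether the analysis needs a valid test.

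**Conclusion.** The concern holds. The 90% belongs to a one-sample pre-post change with the baseline SD standing in for the SD of change. Power for the randomized comparison is not established: with 20 completers per arm it runs from 50% (r = 0.3) to 95% (r = 0.8) for change scores, and from 68% to 97% for ANCOVA. These figures assume a two-sided 5% level, SD 4.0 at both visits and a 3 s difference between arms. The pilot makes the upper part of the range plausible without settling it.

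The problem with the tests does not depend on r: as written, the plan names no test that makes its randomized comparison. This must be fixed.

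**What to change.** Keep N=52 and make two edits before the between-arm analysis is run.

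1. **II.a.** Replace the table and the 90% statement with a two-arm calculation matched to the chosen test. State alpha, sidedness and the SD of change computed from the sponsor's own pilot data, and show power over a range of r. Suggested text: *With 20 completers per arm, SD 4.0 s and two-sided alpha 0.05, power for a 3 s difference between arms by ANCOVA is 76% at r = 0.5, 90% at r = 0.7 and 97% at r = 0.8; the pilot SD of change was [value].* If enrolment is complete, enter this as a dated clarification so that the planning record is preserved.
2. **III.b.** For the six-month Arm 1 versus Arm 2 comparison, name ANCOVA of six-month TUG on baseline TUG and arm, or a two-sample t or rank-sum test on change. Because randomization is within dojo, consider a dojo term. Apply the same correction to the other outcomes in that sentence, and keep paired tests for changes within an arm.

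The cost is one paragraph, one table and one sentence, with no extra patients, visits or data. The stated power becomes conditional on r, and is below 90% with 20 per arm if r is under about 0.70 (ANCOVA) or 0.75 (change score).
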